10.1.3 Demographic Characteristics - Descriptive Statistics

Demographic data presented will be group of DOACs (group A and group B). Demographic data will be summarized using summary statistic for continuous variables (number of subjects, mean, standard deviation, median, minimum, and maximum).

10.1.4 Prior and Concomitant Medications – Descriptive Statistics

Prior and concomitant medications taken by or administered to a subject will be recorded. Prior medications are defined as the medication that started and stopped before Baseline. Concomitant medications are defined as the medications that started before Baseline and continued into the study.

The main medication (i.e. the specific DOAC medication) and the concomitant medication relevant to DOAC therapy will be categorized in groups with ascending numbers (Annex 7). The grouping of concomitant medication may change after descriptive statistics. It is aimed to have a minimum number of n=30 per group.

As the study design is not randomized the two groups will be compared according to biographic data (i.e. age, gender, concentration in urine) by common statistical tests (Chi2 test, t-test) in order to investigate their equality. In the case of differences between groups statistical adjustment will be done (i.e. propensity score) in order to avoid the influence of a bias.

Where that any of the statistical methods described herein prove unsuitable during analysis, more appropriate methods will be used. All changes in methodology will be documented in the clinical study report.

Additional ad-hoc analyses may be conducted as deemed suitable.

Confidentiality Statement

This document is confidential and proprietary to Sponsor and HLZ Medizinische Statistik and for restricted circulation and access only. No part of it may be transmitted, reproduced, published or used by any person/s without prior written authorization.

Table: The treatment label for listings, tables and figures will be the following:

Consecutive number	Treatment	Parameter	Label
1	Group A, Group B	Demographic data dose, duration, and last intake per DOAC	Descriptive statistics, comparison between groups
2	Parameters: FXa DOACs together FXA DOACs individual Creatinine	DOAC Dipstick Reader qualitative and quantitative LC-MS/MS, Jaffe Method	Descriptive statistics
3	Factor Xa Inhibitors together	DOAC Dipstick, LC- MS/MS	Accuracy parameters
4	Thrombin inhibitor	DOAC Dipstick, LC- MS/MS	Accuracy parameters
5 a	Factor Xa Inhibitors Separately Apixaban Edoxaban Rivaroxaban	DOAC Dipstick, LC- MS/MS	Accuracy parameters
5b	Factor Xa Inhibitors separately Apixaban Edoxaban Rivaroxaban Creatinine	DOAC Dipstick, DOASENSE Reader qualitative	Accuracy parameters

Confidentiality Statement

This document is confidential and proprietary to Sponsor and HLZ Medizinische Statistik and for restricted circulation and access only. No part of it may be transmitted, reproduced, published or used by any person/s without prior written authorization.

5c	Factor Xa Inhibitors separately Apixaban Edoxaban Rivaroxaban	DOAC Dipstick, DOASENSE Reader quantitative	Accuracy parameters
5d	Factor Xa Inhibitors separately Apixaban Edoxaban Rivaroxaban	DOASENSE Reader qualitative, DOASENSE Reader quantitative	Accuracy parameters
6	Urine colour, normal and abnormal	DOAC Dipstick, DOASENSE Reader qualitative and quantitative	Descriptive, analysis of difference between groups
7	Factor Xa Inhibitors together Thrombin inhibitor Factor Xa inhibitors separately Apixaban Edoxaban Rivaroxaban	DOAC Dipstick DOASENSE Reader qualitative and quantitative LC-MS/MS	Interaction with demographic data
8	DOASENSE Control urines	DOAC Dipstick, DOASENSE Reader qualitative and quantitative	Descriptive Statistics Analysis of influence on parameters of DOAC Dipstick

Confidentiality Statement

This document is confidential and proprietary to Sponsor and HLZ Medizinische Statistik and for restricted circulation and access only. No part of it may be transmitted, reproduced, published or used by any person/s without prior written authorization.

9	Drop out	Demographic data, withdrawal of consent lack of dose, duration of therapy <7 days, Lack of results of DOAC Dipstick and of DOASENSE Reader No urine samples available at Limbach	Descriptive Statistics
10	Time dependence of results on test parameters	All test parameters of DOAC Dipsick	Descriptive statistics
11	Unexpected results	Examples: Non-compliance (LC_MSMS and DOAC Dipstick both negative) Factor Xa and thrombin inhibitor positive both with DOAC Dipstick and or LC-MSMS	Descriptive statistics
12	Questionnaire	Items	Descriptive Statistics parameters
13	Questionnaire Items	DOAC Dipstick	Interaction analysis

10.1.6 Interim Analysis

No interim analysis will be performed.

10.1.7 Definitions

In the following table, the definitions and calculation of derived variables are summarised.

Confidentiality Statement

This document is confidential and proprietary to Sponsor and HLZ Medizinische Statistik and for restricted circulation and access only. No part of it may be transmitted, reproduced, published or used by any person/s without prior written authorization.

Variable / Term	Definition / Way of calculation
BMI	Weight / Height
Interval therapy duration	Start of therapy - date of last medication intake
Interval urine collection	Date of last medication - Date of urine delivery

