6.3 Study Time points

During a routine visit in the outpatient care unit of the site, patients who match the entry criteria (based on their medical records at the site) will be informed about the Post Marketing Study, and informed consent will be obtained.

Upon patient's written informed consent the investigator will document the patient's demographic characteristics and record the time of last intake of DOAC in the CRF. Then, the patients will provide a sample of urine and give it to the respective site personnel. The patient requires no further action.

The site personnel will put two aliquots of urine (5 mL) into provided test tubes for analysis of the concentration of DOACs and prepare the sample for shipment according to the shipment instructions.

Then, the site personnel will perform the visual and reflectance photometric reading of the DOAC Dipstick.

Thereafter, the site personnel will complete the questionnaire.

Confidentiality Statement

This document is confidential and proprietary to Sponsor and HLZ Medizinische Statistik and for restricted circulation and access only. No part of it may be transmitted, reproduced, published or used by any person/s without prior written authorization.

Assessment	Day 1
Informed consent	X
Demographic data, medical history	X
Medication history (DOACs, other)	X
Collection of urine sample	X
Visual reading presence/absence of DOACs (IVD)	X
Reflectance photometric reading (DOASENSE Reader) of DOAC Dipstick	X
Urine aliquot for bioanalysis (LC_MS/MS)	X
Completion of questionnaire	X

DOACs: direct oral anticoagulants, IVD: *in vitro* diagnostic test

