7.3 Population characteristics

The following data will be recorded for each patient in a CRF:

- Age (years)
- Gender (male, female)
- Body weight (kg)
- Body height (cm)
- Medical and surgical history relevant to DOAC treatment
- Medication history – DOAC (type, dose, start of treatment, last intake before providing urine sample)
- Other medication history relevant to DOAC therapy
- Data will be taken from the patient's medical records.

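### SAP Section 10.1.7 misstates BMI and leaves clock time out of the interval from last intake to urine; read as subtraction, both of its intervals also run backwards

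*SAP*

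**What the plan says.** Section 10.1.7 introduces its table by saying that in it "the definitions and calculation of derived variables are summarised", and the right-hand column is headed as the definition or way of calculation. It has three rows:

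- BMI: "Weight / Height"
- Interval therapy duration: "Start of therapy - date of last medication intake"
- Interval urine collection: "Date of last medication - Date of urine delivery"

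No other section gives a different formula for any of these. Four other places bear on them:

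- Section 7.3 records body weight in kg and body height in cm.
- Section 6.3 tells the investigator to "record the time of last intake of DOAC in the CRF" before the urine sample is given.
- Section 10.1.11 replaces a missing hour and minute of intake with the midpoint of the dosing window, for use in the analysis.
- Section 10.2.2, items VIII and X (the same analysis listed twice), regresses dipstick, reader and LC-MS/MS results on dose, last intake and treatment duration. Table 20 in Section 18 reports dependence on the time of last intake.

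Section 11 states that this SAP prevails where it and the study protocol disagree.

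**The concern.** A derivation table is what the programmer codes from. Each cell here gives an unusable or doubtful result if followed literally. The BMI cell lacks the square and the conversion from centimetres. The urine-interval cell works in calendar dates, while the rest of the plan collects and imputes clock time for the same quantity. Both interval cells put the earlier event first, so as subtractions they run backwards.

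The urine interval matters most. Time since last intake is one of the regressors in items VIII and X and the subject of table 20. Patients on once- or twice-daily dosing differ mainly in the number of hours since the last dose, and a whole-day difference cannot show that. Because the SAP overrides the protocol, a correct definition in the protocol would not repair these cells.

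**Working it through.** The SAP states no numerical result for these variables, so there is no figure to reproduce. I applied the rules literally to illustrative patients; all patient values below are assumed.

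**BMI.** Units are from Section 7.3. For 80 kg and 175 cm:

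- As written, height in cm: 80 / 175 = 0.457
- As written, height in m: 80 / 1.75 = 45.7
- Weight (kg) / [height (m)]²: 80 / 3.0625 = 26.1 kg/m²

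Restoring only the square and keeping centimetres gives 80 / 175² = 0.0026, so the unit must be stated too. The written rule can also change the order of patients:

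| Weight, height | Weight / height (m) | kg/m² |
|---|---|---|
| 80 kg, 160 cm | 50.0 | 31.2 |
| 80 kg, 175 cm | 45.7 | 26.1 |
| 100 kg, 190 cm | 52.6 | 27.7 |

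The third patient has the highest value under the written rule but not under BMI.

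**Urine interval.** The rule is the date of last intake minus the date of urine delivery. The alternative is date-time of urine minus date-time of intake.

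| Last intake | Urine | As written (days) | Hours elapsed |
|---|---|---|---|
| 08:00 | 10:00 same day | 0 | 2.0 |
| 00:30 | 18:00 same day | 0 | 17.5 |
| 23:00 | 08:00 next day | -1 | 9 |
| 20:00 | 08:00 next day | -1 | 12 |
| 08:00 | 08:00 next day | -1 | 24 |
| 08:00 | 16:00 next day | -1 | 32 |

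A value of 0 covers any gap from 0 to just under 24 h. A value of -1 covers anything from just over 0 to just under 48 h. The two ranges overlap, so the variable is not even a reliable ordering: in absolute value the 9 h gap counts as longer than the 17.5 h gap.

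Compare Section 10.1.11. For once-daily intake with no recorded time it assigns 8 p.m., the midpoint between 8 a.m. on the day before sampling and 8 a.m. on the day of sampling. That imputation serves no purpose if only the date enters the interval.

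**Therapy duration.** The rule is start minus last intake.

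- Start 2018-01-15, last intake 2019-01-15: as written -365 days; reversed +365 days.
- A patient at the one-week minimum of Section 7.1: as written -7 days; reversed +7 days.

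**Effect of sign alone.** Replacing a regressor x by -x turns its coefficient b into -b. The standard error, the absolute test statistic, the p-value and the forward-selection path stay the same.

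**The case against.** **The dash may not be a minus.** Both interval rows list the earlier event first, which fits from-to notation. This objection stands in part: the direction is ambiguous rather than certainly wrong. Against it, the column is headed as a way of calculation and the BMI row uses an arithmetic operator, so subtraction is the more natural reading. The from-to reading does nothing for the BMI cell or for the use of dates alone.

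**A superscript may have been lost when the PDF was read.** This cannot be fully excluded, but the digit in Chi2 survives in Section 10.1.5, and the centimetre problem remains either way.

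**Hours are handled elsewhere.** Sections 6.3 and 10.1.11 show that hours are recorded and meant to be used. This stands, and it means the data are not lost. The fault is that Section 10.1.7 contradicts those sections, not that time since intake cannot be analysed.

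**A reader might infer more than the text supports:**

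- *Every interval is negative.* A same-day urine interval is 0.
- *Whole days are too coarse for both intervals.* Days are adequate for therapy duration; only its sign is in question.
- *Every patient would become a drop-out.* The entry "duration of therapy <7 days" in the Section 10.1.5 table belongs to a list of descriptive outputs. Section 10.1.11 has patients with under 7 days of therapy evaluated individually. Nothing applies that limit automatically to the Section 10.1.7 variable.
- *The BMI error distorts named analyses.* BMI appears in no specific analysis, so its use can only be inferred from general references to demographic data. How strongly weight/height would track height in this sample cannot be worked out from the SAP.

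**Conclusion.** The point holds, in order of consequence:

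1. The urine interval is wrong as written because it drops clock time that the plan records and imputes. It takes the value 0 or about -1 day for nearly all patients, assuming intake follows once- or twice-daily dosing, and it can misorder them. This degrades items VIII and X and table 20.
2. BMI is wrong as written: 0.457 or 45.7 instead of 26.1 kg/m² in the example. The effect is limited to whatever demographic summary or regression uses BMI.
3. Under the subtraction reading, therapy duration is negative and the urine interval is zero or negative. Reported coefficients would change sign, but p-values and variable selection would not.

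The primary endpoint uses none of these variables. It would be wrong to conclude that the accuracy results are compromised or that patients would be excluded in error. This is a correction worth making before programming, confined to secondary and descriptive output.

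**What to change.** Rewrite the three cells in Section 10.1.7 and state units and direction:

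- BMI = weight (kg) / [height (m)]², with height converted from centimetres.
- Therapy duration = date of last intake minus date of start of therapy, in days.
- Urine interval = date-time of urine collection minus date-time of last intake, in hours, using the Section 10.1.11 imputation where the intake time is missing.

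State that items VIII and X and table 20 use the interval in hours. Before finalising, confirm that the CRF captures the clock time of urine collection: the SAP provides for recording the time of intake, but the Section 10.1.7 rule refers only to a date of urine delivery.

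The cost is three table cells and one check of the CRF. Intake time is already recorded, and the sample size and primary analysis do not change.

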10.1.8 Analysis Sets

Analysis set	Definition
Per protocol (PP) population	
All patients of the Full analysis population without any relevant protocol violations (major protocol deviations) and complete data for the primary efficacy variable.
 
The relevant protocol violations have to be defined prior to database closure and unblinding by a systematic data review. For this purpose, protocol violations that occurred during the trial such as violations of inclusion/exclusion criteria or forbidden concomitant medications or violation of visit time windows will be assessed as 'major' or 'minor' depending on their potential to interfere with the objectives of the trial.

Major protocol deviations and the assessment of analysis sets will be defined during last data review before data base closure. All definitions given in the Minutes of the Final Data Review will be taken into account in the analysis.

10.1.9 Multicentre Studies

The results will not be stratified by centre in general. The inter-center variability will be analysed.

Confidentiality Statement

This document is confidential and proprietary to Sponsor and HLZ Medizinische Statistik and for restricted circulation and access only. No part of it may be transmitted, reproduced, published or used by any person/s without prior written authorization.

10.1.10 Subgroup Analyses

No subgroup analysis is planned in this trial.

10.1.11 Dropouts and Missing Data

Subject inclusion/exclusion criteria will be determined at baseline visit, and subjects who do not meet all criteria will not be entered into the study. Those subjects with signed informed consent deemed eligible to participate will be allocated a 2-digit number of the center at which patients are recruited followed by a 3-digit number that is consecutive according to the inclusion.

If patients do not fulfil posthoc all inclusion or exclusion criteria – except missing or late signature of written informed consent – e.g. reduced renal function, less than 7 days on therapy, intake of two different DOACs at the same time, change of dose of DOAC within the past 7 days and other findings, they will be evaluated individually and may be described as case reports.

If there is no "informed consent" or if the date of the "informed consent" is after the "start date" it is a dropout.

If a subject withdraws consent at any time after entering the study, will result in patient removal of all data from the study.

If data (dd.mm.yyyy) is specified with 99.99.yyyy in the table, it will be replaced as follows:

1. 99.99.yyyy (day and month missing) is replaced by 01.07.yyyy. Example: 99.99.2017 = 01.07.2017
2. 99.mm.yyyy (day missing) is replaced by 15.mm.yyyy. Example: 99.08.2018 = 15.08.2018

For twice daily intake of medication: If time (hour/min) is not specified, the mean of the time (i.e. 02:00 p.m. or 02:00 a.m., between 08:00 a.m. and 08:00 p.m. or 08:00 a.m. and 08:00 p.m.,

Confidentiality Statement

This document is confidential and proprietary to Sponsor and HLZ Medizinische Statistik and for restricted circulation and access only. No part of it may be transmitted, reproduced, published or used by any person/s without prior written authorization.

whatever applies according the documentation in the CRF, i.e. is taken for the analysis, respectively.

For once daily intake of medication: If time (hour/min) is not specified, the mean of the time (i.e. 08:00 p.m.) between 08:00 a.m. at the day before and the day of urine sampling is taken for analysis.

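### The partial-date rules in SAP 10.1.11 have no bound at the visit and can impute a therapy start after the urine sample, or an apparent duration under 7 days in an eligible patient

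*SAP*

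**What the plan says.** SAP 10.1.11 has two rules for partial dates: "day and month missing) is replaced by 01.07.yyyy" and "99.mm.yyyy (day missing) is replaced by 15.mm.yyyy. Example: 99.08.2018 = 15.08.2018". They are not limited to one date field, so they cover both the start of DOAC therapy and the last intake, which 7.3 records for each patient.

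The same section has two rules for missing clock times. For twice-daily intake the value is a midpoint, "i.e. 02:00 p.m. or 02:00 a.m., between 08:00 a.m. and 08:00 p.m", the choice being "whatever applies according the documentation in the CRF". The once-daily rule begins "For once daily intake of medication: If time (hour/min) is not specified, the mean of the time (i.e. 08:00 p.m" and sets its window from 8 a.m. on the day before up to the day the urine is taken.

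The dates feed two derived intervals in 10.1.7: therapy duration (start minus last intake) and the urine interval (last intake minus urine delivery). Secondary analyses VIII and X in 10.2.2 relate duration and last intake to the test results by forward-selection regression.

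Eligibility requires at least one week of therapy (7.1) and is determined at the baseline visit (10.1.11). Row 9 of the table in 10.1.5 lists "duration of therapy <7 days" under drop-outs. 10.1.11 names under 7 days on therapy among the failures found afterwards, which are assessed case by case.

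**The concern.** A fixed midpoint of the year or month is a reasonable guess when the whole period lies in the past. When the period contains the visit, part of it has not yet happened, and the rule can choose a date in that part. It also discards what the visit established: an enrolled patient had been on treatment for at least a week.

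Two things are at stake. Impossible or badly wrong durations and intake intervals enter analyses VIII and X. An eligible patient can also appear to have had under 7 days of therapy. The per-protocol set is the only analysis set that 10.1.8 defines, breaches of inclusion criteria are graded there as major or minor, and nothing in the SAP says that an imputed date must not be used for that judgement.

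**Working it through.** **The SAP's own values.** The midpoint of 08:00–20:00 is 14:00. The midpoint of 20:00–08:00 is 02:00. The midpoint from 08:00 the day before to 08:00 on the sampling day is 20:00 the day before. 1 July has 181 days before it and 183 after it in a 365-day year. All the stated values reproduce as midpoints.

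**Worked cases.** Duration is taken here as visit minus start, since last intake is on or shortly before the visit day.

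| Recorded start | True start | Visit | True duration | Imputed start | Imputed duration |
|---|---|---|---|---|---|
| 99.99.2018 | 10.01.2018 | 10.03.2018 | 59 days | 01.07.2018 | 113 days after the visit |
| 99.08.2018 | 01.08.2018 | 14.08.2018 | 13 days | 15.08.2018 | 1 day after the visit |
| 99.08.2018 | 01.08.2018 | 20.08.2018 | 19 days | 15.08.2018 | 5 days |

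**Share of possible date pairs, month unknown, start in the visit year.** Number the days 1 to 365. A visit on day d allows d − 7 eligible starts, for d from 8 to 365.
- All eligible pairs: 1 + … + 358 = 358 × 359 / 2 = 64,261.
- 1 July is day 182. The imputed duration is under 7 days when d < 189: 181 × 182 / 2 = 16,471, or 25.6%.
- The imputed start is after the visit when d < 182: 174 × 175 / 2 = 15,225, or 23.7%.

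**Day unknown, start in the visit month.**
- In a 31-day month the eligible pairs number 1 + … + 24 = 300.
- The imputed duration is under 7 days for visits on days 8 to 21: 1 + … + 14 = 105, and 105/300 = 35%.
- Over all months: 7 × 300 + 4 × 276 + 231 = 3,435 pairs, of which 12 × 105 = 1,260 (36.7%) come out under 7 days.
- The imputed start is after the visit in 12 × 28 = 336 pairs (9.8%).

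If the start was in the month before the visit (day unknown), or in an earlier year than the visit (month unknown), no imputed start falls after the visit. In the previous-month case no imputed duration is under 7 days either.

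**Last intake with the day missing.** If the true intake was on the visit day, the 15th falls after the sample for visits on days 1 to 14 of any month: 12 × 14 = 168 of 365 visit days, or 46%.

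**Clock times.** For twice-daily intake, 14:00 on the sampling day is 4 h after a 10:00 sample; 02:00 is before it. For once-daily intake, 20:00 the day before always precedes the sample.

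**The case against.** The case on the other side has force on five points.

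- **Exclusion is not automatic.** A reader might infer that the rules produce false exclusions. The SAP does not say so. Eligibility is settled at the visit, patients failing afterwards are assessed individually, major deviations are judged in a data review, and row 9 is a descriptive table. What remains is a risk, because no text keeps imputed dates out of those judgements.
- **Not every time rule ignores the sample.** The once-daily rule is tied to the sampling day and cannot place the intake after the sample. If the true intake was at 08:00 and the sample was taken at 10:00, it gives 14 h instead of 2 h. That is ordinary midpoint error, not an impossible order. The twice-daily rule leaves the choice to the CRF; it permits the 2 p.m. error without prescribing it.
- **The sign.** A reader might expect misordered dates to show as negative intervals. 10.1.7 subtracts the later date from the earlier, so valid durations are negative and a misordered one is positive (+113 days in the first case).
- **Few patients may be affected.** The trial enrols patients on chronic treatment (8.8), and the time of last intake is recorded at the single visit (6.3). Partial dates in the visit year or month, or a missing day of last intake, may be uncommon. The SAP gives no count.
- **The primary comparison** in 10.2.1 does not use these intervals directly.

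All of this narrows the point. None of it supplies the missing bound.

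**Conclusion.** The partial-date rules are wrong as written. Followed literally, they can place the start of therapy up to months after the visit, or give an apparent duration under 7 days in a patient known to have had more. About 26% of eligible same-year pairs and 35–37% of eligible same-month pairs come out under 7 days. These shares rest on equal weighting of all possible date pairs and apply only to patients whose partial start date falls in the visit year or month. They illustrate the rule and do not forecast the trial.

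The direct effect is on secondary analyses VIII and X. Wrong per-protocol or drop-out classification is possible but not certain. The twice-daily time rule needs tightening; the once-daily rule is not affected. Severity is minor.

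**What to change.** In 10.1.11:

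1. Require start ≤ last intake ≤ urine collection for every imputed date and time. One way is to impute the midpoint between the earliest possible date and the earlier of the latest possible date and the visit date.
2. For twice-daily intake with no time recorded, use the midpoint that precedes the sample.
3. State that an imputed date alone is never used to judge the criterion of under 7 days on therapy.

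**Effect.** With the midpoint in item 1, the visit of 10.03.2018 gives a start of 04.02.2018 (34 days) and the visit of 20.08.2018 gives 10.08.2018 (10 days). No imputed start falls after the visit. Eligible pairs under 7 days fall from 25.6% to 21/64,261 = 0.03% (month unknown) and from 36.7% to 252/3,435 = 7.3% (day unknown). Item 3 deals with the remainder without forcing every imputed duration to at least a week.

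**Cost.** Two or three sentences in the SAP and a few lines of code. The order check must follow the direction of subtraction in 10.1.7, where a misordered pair shows as a positive value.
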